5.4 Reporting Timeline

- Within **24 hours** (of learning of the event), investigators will report any reportable Serious Adverse Event (SAE) that:
 - Is considered life-threatening/disabling or results in death of subject
 - OR-
 - Is Unexpected/Unanticipated
- Investigators will report all other reportable SAEs within **5 working days** (of learning of the event).
- All other (suspected) reportable AEs will be reported to the RDCRN within **20 working days** of the notification of the event or of the site becoming aware of the event.

Any SAE or Special Situations Reports (SSR) will also be reported to the Gilead Drug Safety and Public Health department within 15 days of learning of the event. Redacted SAE/SSR reports are preferred by email at the following contact information:

Gilead Sciences, Inc.
Drug Safety and Public Health
[name]
[name]
[contact]
[contact]

Email: Safety [contact]

Local institutional reporting requirements to CIRB, any GCRC oversight committee and the FDA, if appropriate, remain the responsibility of the treating physician and the Study Chair.

5.5 RDCRN DMCC Adverse Event Monitoring Process

The DMCC will make adverse event reports available for review. Upon entry of a serious adverse event (SAE) into the DMCC database, the Study Chair, site PIs, the RDCRN D/OSMB medical review officer, and any additional agencies (if applicable-industry sponsor) will be notified immediately by email.

Serious adverse events: The NIH appointed Medical Review Officer (MRO) reviews the site investigator's report and determines causality (definitely not related, probably not related, possibly related, probably related, definitely related) of the adverse event. The MRO may request further information if necessary and possibly request changes to the protocol or consent form as a consequence of the adverse event. Any follow up reports or requested additional participant data will be entered into the DMCC Adverse Event Monitoring System by the reporting site and reviewed by the MRO. Completed AE reviews by the MRO will be sent to Study Chair, site PIs, and the appointed NIH officers.

If warranted, the MRO may request an ad hoc call with the DSMB to review the adverse event. All reported AE's will be reviewed during the regularly scheduled DSMB call. The DMCC Adverse Event Monitoring Process maintains audit trails and stores data (and data updated) and communication related to any adverse event in the study.

Non-serious expected adverse events: Except those listed above as immediately reportable, non-serious adverse events that are reported to or observed by the investigator or a member of his research team will be submitted to the system in a timely fashion (within 20 working days). The events will be presented in tabular form and given to the MRO and RDCRN D/OSMB on an annual basis. Local site investigators are also required to fulfill all reporting requirements of their local institutions.

The DMCC will post aggregate reports of all adverse events (serious/not serious and expected, unexpected) for the DSMB, site investigators and CIRB.

5.6 Study Discontinuation

The NIH, RDCRN DSMB, and CIRB have the authority to stop or suspend this trial at any time. This study may be suspended or closed if:

- The study objectives have been met
- The Study Chair / Study Investigators believe it is not safe for the study to continue
- The RDCRN DSMB suspends or closes the trial
- The NIH suspends or closes the trial
- The FDA suspends or closes the trial
- Gilead Sciences elects to suspend or close the trial

5.7 Subject Discontinuation

An intent to treat approach will be used. All data acquired prior to termination for the reasons outlined below will be included in the primary analysis. Every effort will be made to conduct a final study visit with the participants and participants will be followed clinically until, if applicable, all adverse events resolve.

- Withdrawal of consent by the participant
- Withdrawal by the investigator if early stopping rules have been met: If there are Grade 4 toxicities, such as severe bradycardia with syncope, Harvoni will be stopped. Subject's PCT symptoms worsen significantly (as specified in section 5.3)
- Withdrawal by the investigator for other reasons
- Intercurrent illness or event that precludes further visits to the study site or ability to evaluate disease (e.g. mental status change, large pleural effusion).

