The therapy will be Harvoni at the usual dose (90 mg of ledipasvir and 400 mg of sofosbuvir) and duration for CHC therapy. One tablet taken daily for 8 weeks for patients without cirrhosis, not previously treated with HCV GT1 and HCV RNA < 6 million IU/mL; 12 or 24 weeks, duration to be determined based upon clinical features and prior treatment experience. 8 or 12 weeks for subjects with or without cirrhosis, not previously treated with anti-virals for CHC, and 24 weeks for subjects with cirrhosis who were previously treated with anti-virals for CHC without having achieved SVR. During the first year study visits will be monthly, and this includes the treatment period of either 12 or 24 weeks. To assess cure of HCV infection, repeated HCV RNA levels at 3, 6, and 12 months after end of Harvoni therapy will be done, as well as annually thereafter. Evaluation by a hepatologist at follow up visits will be as needed, determined by the screening lab test results and by clinical and lab findings at follow-up visits.

Lab measures to be checked monthly during therapy will include CBC, CMP, plasma total porphyrins, urinary total porphyrins (with HPLC), and levels of HCV RNA in serum by quantitative PCR (Section 4.7 Schedule of Events).

Porphyrin specific lab tests will be performed at the UTMB Porphyria Laboratory; all other labs will be performed at Covance Laboratories.

Subjects who have their treatment discontinued for any reason will continue to be followed until the end of the study, including longer-term follow up visits, unless they withdraw consent. If a subject becomes pregnant during the study Harvoni will be discontinued. The outcome of the pregnancy will not be followed as part of this study. Pregnancy during the study should be reported as an SAE.

Longer-Term Follow-up:

12 months after beginning treatment, subjects will be asked to return every four months for one year, with repeat of interval history and physical examination (especially to reassess the status of cutaneous lesions of PCT) and the above studies.

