Worsening PCT symptoms: PCT is a rare disease and no standard disease severity scale exists. A standardized detailed skin assessment including pictures will be done at each time point in this study. If a subject experience significantly worsening symptoms in the opinion of the investigator that persist for 60 days, HCV therapy will be discontinued under the study and standard of care PCT treatment will be initiated. This length of time may be shortened depending on the severity of the subject’s PCT symptoms. Any patient who experiences worsening PCT symptoms must be discussed by the site PI with the Study Chair prior to discontinuing Harvoni.

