If data are missing due to severity of illness, the patient will be counted as a treatment failure (i.e. resolution not achieved). Patients with missing primary outcome data not due to severity of illness will have their 7 month resolution status imputed via multiple imputation assuming that the data are missing at random (i.e. the missing nature of the variable is independent of the value of the variable given the observed data). The specific imputation model to be used will be determined prior to examination of any outcome data, but will include any measured plasma porphyrins from baseline to 6 months. Imputed data will be rounded to 0 (failure/resolution not achieved) or 1 (success/resolution achieved).

After the imputations are completed, all of the data (complete and imputed) will be combined and the analysis performed for each imputed-and-completed dataset. Rubin's method of multiple (i.e., repeated) imputation will be used to estimate treatment

effect. We propose to use 15 datasets (an odd number to allow use of one of the datasets to represent the median analytic result).

Secondary Endpoints:

Time to resolution of active PCT, defined as normalization of plasma porphyrins (less than 0.9 mcg/dL): The median time to resolution by this definition will be computed using Kaplan-Meier estimation and compared descriptively to the median time to resolution reported by standard therapies.

Time to resolution of active PCT, defined as cessation of any new blisters or bullae: Complete resolution of skin manifestations is expected to occur later than normalization of plasma porphyrins, because it takes time for healing of the skin fragility that predisposes of blister formation to occur. The median time to resolution by this definition will be computed using Kaplan-Meier estimation and compared descriptively to the median time to resolution reported by standard therapies.

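### Sections 4.6 and 5.7 conflict on whether subjects who meet a stopping rule stay in scheduled follow-up, and section 6 does not class their missing Month 7 status

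*Combined protocol and SAP*

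**What the plan says.** Section 4.6 (Treatment and Follow-up Visits) is explicit: "Subjects who have their treatment discontinued for any reason will continue to be followed until the end of the study". Its long-term visits are covered too, and the only exception it names is withdrawn consent.

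Section 5.7 (Subject Discontinuation) announces an intent-to-treat approach and then lists reasons for termination. Beside withdrawn consent and inability to attend or be evaluated stands "Withdrawal by the investigator if early stopping rules have been met: If there are Grade 4 toxicities". The same bullet adds significant PCT worsening and refers to section 5.3. For all listed reasons, 5.7 says: "All data acquired prior to termination for the reasons outlined below will be included in the primary analysis". It provides for one closing visit: "Every effort will be made to conduct a final study visit with the participants". Safety follow-up after that visit is clinical and lasts until any adverse events have resolved.

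Yet both stopping rules are worded as stopping the drug. For Grade 4 toxicity, 5.7 says that Harvoni is stopped. For worsening PCT, 5.3 says "HCV therapy will be discontinued under the study and standard of care PCT treatment will be initiated".

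Section 6 counts a missing primary outcome as a failure if severity of illness is the cause. Otherwise, "Patients with missing primary outcome data not due to severity of illness will have their 7 month resolution status imputed via multiple imputation", on a missing-at-random assumption.

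**The concern.** Section 4.6 treats stopping the drug and leaving the study as two events. Section 5.7 appears to treat them as one. A site working from 5.7 could close a subject out after a final visit; a site working from 4.6 would continue the 4.7 visits to Month 24.

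The subjects concerned are those with severe toxicity or worsening PCT, so any loss of data is related to outcome. What can be lost is the monthly plasma porphyrin series up to Month 7 (primary endpoint), HCV RNA after the end of treatment (the cure endpoint needs at least 12 weeks) and the later relapse visits. Durability is part of the aim in section 2, and section 3 cites reports of anti-viral therapy precipitating or worsening PCT, so the event is foreseeable.

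Section 6 assigns neither stopping rule to failure or to imputation. The primary result could therefore depend on which section a site followed and on how the analyst reads an undefined term.

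**Working it through.** **1. The passages side by side**

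| Question | 4.6 | 5.7 |
|---|---|---|
| Event | treatment stopped for any reason | investigator withdrawal when a stopping rule is met |
| Visits afterwards | to study end, longer-term visits included | a final visit, on best effort |
| Safety follow-up | through the scheduled visits | clinical, until adverse events resolve |
| Data named for the primary analysis | not addressed | data acquired before termination |

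Because 5.7 and 5.3 describe both rules as stopping the drug, these subjects fall under 4.6 as well. A final visit has no clear purpose if visits run on to Month 24, so the two sections do not fit together as written.

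**2. The plan's own figure**

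Inputs (section 6): N = 49, null 0.40, true rate 0.58, one-sided 0.05, success if 26 or more resolve.

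- Power: P(Bin(49, 0.58) ≥ 26) = 0.8015, matching the stated 80.2%.
- Type I error: P(Bin(49, 0.40) ≥ 26) = 0.0439. Table 3 prints 0.0434; its other five rows agree. The difference does not affect this point.

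**3. Leverage of one subject**

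The exact one-sided 95% lower bound is the 5% quantile of Beta(x, 49 − x + 1).

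- x = 26: Beta(26, 24) gives 0.404, above 0.40, so non-inferiority is declared.
- x = 25: Beta(25, 25) gives 0.385, so it is not.

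Each subject is 1/49 = 2.0 percentage points.

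**4. How many subjects**

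The label data in 5.3 give discontinuation for adverse events of 0%, <1% and 1% at 8, 12 and 24 weeks. At most 0.01 × 49 = 0.49 subjects would be expected. No rate is given for stopping because PCT worsens.

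**5. Illustration of the classing rule**

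The number withdrawn, k, is an assumption, shown for 0 to 3.

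(a) The k subjects count as failures and the rest succeed at 58%: power = P(Bin(49 − k, 0.58) ≥ 26).

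(b) The true overall rate is 0.40 and the k subjects are all true failures. Completers then succeed at q = 0.40 × 49/(49 − k). If the k subjects are imputed at q, the chance of a false positive is P(Bin(49, q) ≥ 26). If they count as failures, it is P(Bin(49 − k, q) ≥ 26).

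| k | (a) power | q | (b) imputed at q | (b) counted as failures |
|---|---|---|---|---|
| 0 | 80.2% | 0.400 | 4.4% | 4.4% |
| 1 | 75.4% | 0.408 | 5.6% | 4.3% |
| 2 | 70.0% | 0.417 | 7.2% | 4.1% |
| 3 | 64.0% | 0.426 | 9.2% | 4.0% |

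In (a) part of the fall reflects an overall success rate that is itself below 58%. The imputed column in (b) is an unfavourable case. It treats imputation as a single draw, ignores the between-imputation variance in Rubin's method, and ignores each subject's own earlier porphyrins, which section 6 puts in the imputation model.

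**The case against.** The best defence is that the sections can be read together. Section 4.6 is unambiguous, 5.3 and 5.7 describe stopping the drug, 5.7 opens with intent to treat, and it never says in terms that scheduled visits cease. That reading is available, but 5.7 still places these subjects under withdrawal and termination, beside withdrawn consent, so a site cannot be relied on to choose it.

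Several stronger readings are tempting, and the documents do not support them:

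- *All safety follow-up is lost.* It is not. Section 5.7 continues clinical follow-up until adverse events resolve. What is exposed is scheduled follow-up and the detection of later events.
- *Only data from before termination are analysed.* Section 5.7 says that such data are included; it does not exclude later data.
- *Anyone withdrawn before Month 7 has no primary outcome.* The endpoint is resolution by 7 months and porphyrins are measured monthly, so a subject who normalised earlier may already have met it.
- *Several subjects will be affected.* An assumed 5–10% worsening rate would give 0.05 × 49 = 2.5 to 0.10 × 49 = 4.9 subjects, but nothing in the documents supports that rate.

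There are also real safeguards. Section 6 promises reasons for missing data and sensitivity analyses, with best-case and worst-case scenarios as examples. Section 5.3 requires discussion with the Study Chair before Harvoni is stopped for worsening PCT, which limits variation between sites for that rule. Worsening PCT could well be read as severity of illness and so as failure. These safeguards reduce the risk, but they do not settle the primary classification or recover a value that could have been measured.

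One objection bears on the remedy. If follow-up simply continues and all data count, normalisation under the standard PCT treatment started under 5.3 could pass as a Harvoni success in a sole-therapy trial. That stands, and the fix has to deal with it.

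**Conclusion.** The point holds as a conflict of wording with a consequence for the primary analysis. Sections 4.6 and 5.7 give different dispositions for a subject who meets a stopping rule, and section 6 leaves a resulting missing Month 7 status unclassed. The expected number is small for adverse events (at most about 0.5 of 49 on label rates) and unknown for PCT worsening. The effect matters only when the count lies near 26, where one subject can move the decision. The power and false-positive figures for k above 0 are illustrations under assumed k, not predictions. The stated N, power and decision rule are unaffected.

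**What to change.** 1. In 5.7, separate end of study drug from end of study participation, with a separate CRF date and reason for each. State that stopping drug does not by itself end the 4.7 visits, in line with 4.6.
2. Reserve termination and the final visit for withdrawn consent or inability to attend or be evaluated.
3. In section 6, state whether a subject who met either stopping rule and has no Month 7 value is a failure or is imputed.
4. In section 6, state that normalisation first reached after standard PCT treatment has started does not count as a Harvoni success in the primary analysis.

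The clinical stopping rules themselves are not to be changed by this edit.

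Cost: minor wording and CRF work. The visits already stand in the 4.7 schedule, though the documents give no budget from which to confirm funding. The observed success rate may become slightly less favourable. N = 49 and the 26-of-49 rule stay as they are.

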5.8 Data Quality and Monitoring Measures

As much as possible data quality is assessed at the data entry point using intelligent on-line data entry via visual basic designed screen forms. Data element constraints; whether independent range and/or format limitations or 'relative' referential integrity limitations can be enforced by all methods employed for data input. QA reports assess data quality post-data entry. As we note, data quality begins with the design of the data collection forms and procedures and incorporates reasonable checks to minimize transcription and omission errors. Of the more important quality assurance measures are the internal validity checks for reasonableness and consistency.

- Data Monitoring: The RDCRN DMCC identifies missing or unclear data and generates a data query to the consortium administrator contact.
- Data Delinquency Tracking: The Data Management and Coordinating Center will monitor data delinquency on an ongoing basis.

5.9 Quality Control: Study Related Procedures

The standard laboratory measures will be performed at each Covance Central Laboratory. Porphyrin measurements will be performed in the CLIA certified laboratory of [name], University of Texas Medical Branch, Galveston, TX (see Appendix I for processing instructions).

The investigational pharmacy at each site will be responsible for drug accountability while the investigators/coordinators will be responsible for compliance of the subjects. The Investigational Drug Service at Wake Forest University will serve as the coordinating pharmacy for this study.

6. Statistical Considerations

Primary endpoint: The primary endpoint is resolution of active PCT, defined as normalization of plasma porphyrins (less than 0.9 mcg/dL) by 7 months after the start of therapy. The primary hypothesis will be assessed by computing the exact (i.e., based on the binomial distribution) lower one-sided 95% confidence bound for the proportion of patients whose PCT resolves by 7 months. If this lower confidence bound exceeds 0.40 (the performance goal of 0.50 minus the non-inferiority margin of 0.10) then Harvoni will be declared non-inferior to the performance goal. Seven months has been chosen based upon recent results comparing iron reduction and hydroxychloroquine as therapy for PCT (Singal et al, 2012) and on the consensus of the investigators of the Porphyrias Consortium that a median time to resolution of 7 months would cause them to consider using Harvoni over phlebotomy or hydroxychloroquine as a first line of treatment for PCT patients with Hepatitis C.

Patients missing primary endpoint data are a potential problem in all clinical trials, with the potential for biased inference increasing with the amount of missing outcome data. We will report reasons for missing data, and examine the effect that any missing data might have on results via sensitivity analysis of augmented data sets (for example, best-case or worst-case scenarios). Patients missing the trial's primary endpoint will be included in the analysis by modern imputation methods for missing data.

If data are missing due to severity of illness, the patient will be counted as a treatment failure (i.e. resolution not achieved). Patients with missing primary outcome data not due to severity of illness will have their 7 month resolution status imputed via multiple imputation assuming that the data are missing at random (i.e. the missing nature of the variable is independent of the value of the variable given the observed data). The specific imputation model to be used will be determined prior to examination of any outcome data, but will include any measured plasma porphyrins from baseline to 6 months. Imputed data will be rounded to 0 (failure/resolution not achieved) or 1 (success/resolution achieved).

After the imputations are completed, all of the data (complete and imputed) will be combined and the analysis performed for each imputed-and-completed dataset. Rubin's method of multiple (i.e., repeated) imputation will be used to estimate treatment

effect. We propose to use 15 datasets (an odd number to allow use of one of the datasets to represent the median analytic result).

Secondary Endpoints:

Time to resolution of active PCT, defined as normalization of plasma porphyrins (less than 0.9 mcg/dL): The median time to resolution by this definition will be computed using Kaplan-Meier estimation and compared descriptively to the median time to resolution reported by standard therapies.

Time to resolution of active PCT, defined as cessation of any new blisters or bullae: Complete resolution of skin manifestations is expected to occur later than normalization of plasma porphyrins, because it takes time for healing of the skin fragility that predisposes of blister formation to occur. The median time to resolution by this definition will be computed using Kaplan-Meier estimation and compared descriptively to the median time to resolution reported by standard therapies.

Complete Biochemical remission of PCT: Complete biochemical remission of PCT will be measured as a decrease of the sum of urinary uro- and hepta-carboxyl porphyrins to less than 100 mcg/g creatinine, and a normal urine porphyrin HPLC pattern, defined as the total of highly carboxylated porphyrins (uro- and heptacarboxyl-porphyrins) being less than that of coproporphyrins, and absence of a fluorescence peak by fluorescence scanning. The proportion of patients who achieve complete biochemical remission by the end of study period will be computed and the median time to resolution by this definition will be computed using Kaplan-Meier estimation. Because of underlying liver disease and/or possible continuing alcohol use, total urinary porphyrins may remain elevated, due to increased coproporphyrins. We will explore whether and to what extent total urinary porphyrins may remain elevated, due to increased coproporphyrins descriptively in these subjects.

Cure of CHC: Cure of CHC will be defined as no detectable HCV RNA at end of treatment (EOT) and persisting for at least 12 weeks after EOT, now taken as usual definition of sustained virological response (SVR). The proportion of patients who achieve CHC cure will be reported.

Sample Size: The primary study hypothesis is that the proportion of patients whose PCT resolves by 7 months will be non-inferior to the performance goal of 50%. This performance goal is based on previously published data that reported a median time to resolution between 6-7 months for PCT patients undergoing treatment with iron reduction by therapeutic phlebotomies or hydroxychloroquine (Singal et al, 2012). The non-inferiority margin will be set to 10%; a difference from the performance goal judged to be both clinically acceptable and well within the margin needed to assure that the performance of Harvoni is at established levels of benefit from conventional therapies. Thus, the null hypothesis tested by this study is $H_0: \pi \leq 0.40$, against the alternative hypothesis $H_1: \pi > 0.40$.

Sample size requirements are based on an exact test of a binomial proportion. Assuming that the study drug has a true success probability of 58%, 49 subjects yield 80% power to reject the null hypothesis at a one-sided significance level of 0.05.

The null hypothesis would be rejected at the final analysis if 26 or more successes out of 49 subjects were observed (an observed success rate of 53.1%). The power of the test assuming a true success rate of 58% for Harvoni is 80.2%. Operating characteristics for the decision rule corresponding to the final analysis are given below (Table 3).

Table 3: Operating characteristics for the decision rule (Final analysis)

True Harvoni success rate (π)	Prob (26 or more successes π , N=49)
0.40	0.0434
0.45	0.1609
0.50	0.3877
0.55	0.6627
0.60	0.8718
0.65	0.9695

7. Data Management

As much as possible, data quality is assessed at the data entry point using intelligent on-line forms via the DMCC. Data element constraints; whether independent range and/or format limitations or 'relative' referential integrity limitations can be enforced by all methods employed for data input. QA reports assess data quality post-data entry. As we note, data quality begins with the design of the data collection forms and procedures and incorporates reasonable checks to minimize transcription and omission errors. Of the more important quality assurance measures are the internal validity checks for reasonableness and consistency. In addition to those described above, we propose to build these checks into the initial tables and cross tabulations that should reveal any remaining data quality issues. The NIH Program Staff, the DMCC, and Porphyrias Consortium staff are responsible for assuring and monitoring data quality.

All study data will be collected via systems created in collaboration with the RDCRN Data Management and Coordinating Center and will comply with all applicable guidelines regarding patient confidentiality and data integrity.

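### Only undefined illness severity makes a missing outcome a failure, so a patient lost after toxicity or for lack of PCT benefit can be imputed as a success

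*Combined protocol and SAP*

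**What the plan says.** All references are to the combined protocol and SAP.

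- **Section 6, failure rule.** "If data are missing due to severity of illness, the patient will be counted as a treatment failure (i.e. resolution not achieved". The plan does not say what the term covers or who decides.
- **Section 6, everything else.** "Patients with missing primary outcome data not due to severity of illness will have their 7 month resolution status imputed via multiple imputation", under MAR. The model is to be fixed before outcome data are examined and must use the plasma porphyrins available up to month 6. Imputed values are rounded to 0 or 1, and 15 datasets are combined by Rubin's method.
- **Section 6, safeguards.** Reasons for missing data will be reported. Best-case and worst-case analyses are mentioned, but only as examples of sensitivity analysis.
- **Section 6, decision.** The exact one-sided 95% lower bound decides: "If this lower confidence bound exceeds 0.40", non-inferiority is declared. In counts: "The null hypothesis would be rejected at the final analysis if 26 or more successes out of 49 subjects were observed".
- **Section 5.7.** Subject discontinuation covers consent withdrawal, investigator withdrawal for toxicity or significant PCT worsening, other investigator reasons and intercurrent illness. On toxicity: "If there are Grade 4 toxicities, such as severe bradycardia with syncope, Harvoni will be stopped". Data up to termination are analysed, and a final visit is to be attempted.
- **Section 4.6.** Patients whose treatment stops, whatever the reason, stay in follow-up to the end of the study unless they withdraw consent.

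**The concern.** Section 5.7 foresees losses linked to the drug or to the disease, yet Section 6 names only one ground for scoring a loss as failure. Someone who withdraws consent because the skin disease is not improving, or who is withdrawn after toxicity and not seen again, falls by default into MAR imputation and may be drawn as a success.

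This matters more here than in a randomized trial. The comparison is with a fixed 0.40, so no control arm is handled the same way to offset the error. The 26-of-49 rule also leaves little room below 0.05. The worst-case analysis would show the problem, but it does not decide the claim.

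**Working it through.** **Inputs from Section 6.** N = 49; threshold 0.40 (goal 0.50 minus margin 0.10); one-sided level 0.05; reject at 26 or more successes; assumed true rate 0.58; stated power 80.2%.

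**Reproducing the plan.** For X ~ Binomial(49, 0.58), P(X ≥ 26) = 0.8015, which agrees with 80.2%. The exact lower bound is 0.4043 for 26/49 and 0.3847 for 25/49, so the cutoff of 26 is right. At 0.40, P(X ≥ 26) = 0.0439. Table 3 prints 0.0434; this small slip does not affect the rule.

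**Assumptions.** The plan states no dropout rate. Let k patients have outcomes missing for reasons not classed as illness severity, and let all k be true failures. Hold the overall true rate at 0.40. The completers' rate is then

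pc = 0.40 × 49 / (49 − k).

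Let q be the chance that a lost patient is imputed as a success. A low q (0.10) means the observed porphyrins reveal the non-response. q = pc means they carry no information.

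**Formula.** With J ~ Binomial(k, q) imputed successes and X ~ Binomial(49 − k, pc) observed successes,

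type I error = Σⱼ P(J = j) × P(X ≥ 26 − j).

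**Example, k = 1.** pc = 0.40 × 49/48 = 0.4083. The chance of a win is 0.0426 if the patient is scored a failure and 0.0760 if scored a success.

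- q = 0.10: 0.90 × 0.0426 + 0.10 × 0.0760 = 0.046
- q = pc: 0.5917 × 0.0426 + 0.4083 × 0.0760 = 0.056

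| k lost (of 49) | pc | scored failure | q = 0.10 | q = 0.20 | q = pc |
|---|---|---|---|---|---|
| 1 | 0.408 | 0.043 | 0.046 | 0.049 | 0.056 |
| 2 | 0.417 | 0.041 | 0.048 | 0.055 | 0.072 |
| 3 | 0.426 | 0.040 | 0.050 | 0.062 | 0.092 |
| 5 | 0.446 | 0.037 | 0.055 | 0.076 | 0.146 |

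**Check with 15 imputations.** The formula uses a single draw per lost patient. A simulation of 200,000 trials with 15 imputations and uninformative porphyrins (the q = pc case) gives, for k = 1, 2, 5:

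- rule applied to the median dataset: 0.061, 0.074, 0.163
- Rubin's rules with a Wald bound: 0.067, 0.074, 0.148

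These are of the same order as the last column.

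**If MAR is true.** Lost patients then resolve at the rate at which they are imputed (0.40), and the error stays at 0.0439 for any k.

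**How common toxicity stops might be.** Section 5.3 reports permanent discontinuation for adverse events of 0%, <1% and 1% for 8, 12 and 24 weeks. At 1%, 0.01 × 49 = 0.49 patients are expected, and the chance of at least one is 1 − 0.99^49 = 0.39. The documents give no rate for withdrawal over lack of benefit.

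**The case against.** The case for leaving the text alone has five parts.

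1. **Stopping the drug is not a missing outcome.** A reader might infer from Section 5.7 that every toxicity stop ends in imputation. Section 4.6 says otherwise: follow-up continues unless consent is withdrawn, and Section 4.7 schedules porphyrins monthly to month 12. This stands, and toxicity stops were rare in the earlier trials. It does not cover patients who withdraw consent. Section 5.7 also treats toxicity and PCT worsening as grounds for withdrawing the subject, so the two sections do not agree on whether data collection continues.
2. **The model sees the endpoint variable.** Monthly porphyrins pull a visible non-responder towards failure, and at q = 0.10 the inflation is small. This stands, except for early leavers with few values.
3. **Leaving over skin symptoms need not mean failure.** The primary endpoint is plasma porphyrin alone, and the plan expects skin healing to lag behind it. Such a patient might have met the endpoint. This stands: true failure is an assumption in the table above.
4. **Worsening PCT may already count.** A reader might infer that the failure rule catches only unrelated intercurrent illness. The text does not support that, because illness severity in a PCT trial can reasonably include worsening PCT. The defect is the missing definition, which leaves the choice to be made patient by patient.
5. **MAR with sensitivity analyses is a recognised approach.** Fair, but those analyses are only examples and do not decide the claim.

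**Conclusion.** The point holds in conditional form. As written, the deciding analysis can score as a success a patient who was lost after toxicity or for lack of PCT improvement.

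Inflation needs three things together: a Month 7 outcome that is actually missing, a true failure, and porphyrins to month 6 that do not reveal it. Given all three, one such patient takes the error past 0.05 only if imputed at close to the completers' rate. Two do so at q = 0.20, and five do so even at q = 0.10. The numbers lost are assumptions throughout.

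It would be tempting to say that the plan is biased toward a win. The documents do not support this without the conditions: under true MAR there is no inflation, and neither the number lost nor how they would be imputed can be read from the text. The gap is worth closing because the effect falls directly on the decision and the repair is cheap.

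**What to change.** In Section 6:

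- State that a patient with no plasma porphyrin value below 0.9 mcg/dL and no Month 7 value is a failure if follow-up ended because of death, severity of illness, an adverse event, or lack of improvement or worsening of PCT.
- Limit multiple imputation to outcomes missing for reasons unrelated to drug or disease, such as a missed visit, relocation or a lost sample.
- Have each reason classified before outcomes are examined.
- Make the analysis that scores all missing outcomes as failures mandatory.

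Reconcile Sections 4.6 and 5.7 on whether follow-up, including the Month 7 sample, continues after such withdrawals.

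**Cost.** If the lost patients are failures, the type I error stays below 0.05 (0.043, 0.041 and 0.037 for one, two and five). If some would have resolved, for example a patient who leaves with porphyrins just above 0.9 and falling, the success rate and power drop. As an illustration, take a share d scored as failures although they would have resolved at 0.58. The effective rate is 0.58 × (1 − d), and power with 49 patients falls from 80.2% to 77.8% at d = 1%, 75.2% at 2% and 66.8% at 5%. Here d counts only losses related to drug or disease, so it should be smaller than total dropout.
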